**The goal of the proposed study is to examine the abuse liability and substitutability of plausible menthol cigarette alternatives.** Using an in-laboratory and *ad libitum* outpatient mixed design, current menthol cigarette smokers (N=135) will complete a three phase, 3-week study: in Phase 1, utilizing a randomized crossover design, participants will complete [4 smoking sessions], smoking a different product each session to examine each product's abuse liability, demand, and topography. Products will include participants' usual brand menthol cigarette (UBMC) as well as 3 commercially-available alternatives, including mFLC, mRYO product, [*and non-mentholated cigarette (nmC).*] Participants will complete one-week of daily diaries after smoking session 1 in phase 1 to assess their usage of usual brand menthol cigarette (UBMC). In Phase 2, to assess uptake, changes in subjective effects, and use over time, participants will [*select their preferred study product from Phase 1*] and be instructed to completely substitute the product for their UBMC for one week. Participants will complete daily diaries during this period to more accurately assess substitution and perceived effects in real-time. In Phase 3, participants will complete a final in-lab visit to assess the substitutability of [*their preferred product from Phases 1 and 2,*] under simulated ban conditions using a progressive ratio task. In all phases, multiple domains of abuse liability will be assessed, including product administration (in-lab topography and daily diary self-report measures), product liking/craving and withdrawal suppression (in-lab and daily diary self-report).

**Aim 1: To assess the abuse liability of menthol cigarette alternatives.** *H1a: Alternatives will [have similar use topography and significantly reduce nicotine craving/withdrawal similar to UBMC, but (H1b) UBMC will show significantly greater demand indices and liking/satisfaction compared to alternatives. H1c: Among alternatives, nmC will show the greatest demand and liking/satisfaction, followed by mFLC, and lastly mRYO.]*

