## Addiction and Behavior Related to Menthol Cigarette Substitutes

12 hours of overnight tobacco abstinence, biochemically verified by exhaled carbon monoxide ( $eCO \leq 10\text{ppm}$ ). Sessions will be separated by a standard 48-hour washout period. Participants will smoke one cigarette ad libitum and a puff topography device will discretely record smoking behavior throughout the session, including puff duration, number of puffs, puff volume, and time between puffs.  $eCO$ , and self-report measures of craving and withdrawal will be recorded immediately before and at several times after the smoking session. Self-report measures of abuse liability will also be completed during the sessions. During the preferred study product observational use period, participants will be provided a weeks' worth of a potential menthol substitute at no cost. Consistent with our previous switching studies, study products will be provided in a 1.2 to 1 ratio based on self-reported use at the time of screening. This slight over appropriation helps to ensure that participants have enough study product available so to not artificially limit use, while also not oversupplying and potentially artificially increasing use behind what would be usual. Participants will be instructed to completely switch and exclusively use the study product during the 1-week time period. During this period, participants will complete daily diary once a day. Following the one-week use period, participants will come to the lab following 12-hr nicotine abstinence confirmed by  $eCO$ . To simulate the effect that restricting menthol in cigarettes would have on increasing (or not) preference for other alternative menthol substitutes, participants will complete a 90-minute concurrent choice task with differential cost (effort) required to earn 2 puffs from their UBMC (10 clicks increasing to 7200) versus their preferred study product (always 10 clicks) from Phase 2. . This session will last approximately 3 hours.

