### Detailed Study Procedures

**UBMC and Study Product Lab Sessions (Phase 1):** Upon arrival at the lab, 12-hr tobacco abstinence will be assessed via self-report and confirmed with exhaled carbon monoxide testing ( $eCO \leq 10\text{ppm}$ ). Pregnancy exclusion will also be confirmed with a urine test; and breath alcohol concentration (BrAC) tests will ensure  $BrAC < .01$ . Participants will not be allowed to eat or drink (other than water) during the session. Participants will be instructed to smoke one UBMC or study product *ad libitum* to completion through a puff topography device.  $eCO$  will be collected immediately pre- and post-smoking. Measures of subjective effects (see Table 1) will be collected immediately before the onset of puffing and at 1-min, 15-min, 30-min, 60-min, and 90-min after completion of the cigarette. The Cigarette Purchase Task will also be completed during the lab sessions. Sessions will last

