## Addiction and Behavior Related to Menthol Cigarette Substitutes

### 3. Measures

Questionnaire data will be collected over the phone or in-person by a trained research assistant and data will be entered into a secured and encrypted database using REDCap. See Table 1 for timing of measures. Sociodemographic measures will assess participant age, sex, marital status, ethnicity, employment status, occupation, years of education, and socioeconomic status. Tobacco use history will assess years of smoking, age of smoking onset, average number of cigarettes per day, number and recency of previous 24-hour quit attempts, number of smokers in the household, prior use of nicotine replacement therapy and other stop smoking medications, and history of receiving smoking cessation counseling. It will also assess tobacco type, brand, frequency, quantity, and duration of use all of nicotine/tobacco products including cigars, cigarillos, little cigars, pipe tobacco, chewing tobacco, snuff, snus, EC/vape/mod/APV/e-hookah, combusted tobacco hookah, and dissolvable tobacco. Cigarette Dependence will be measured with the 12-item Cigarette Dependence Scale. Exhaled carbon monoxide will be assessed at the start of each study visit. Abuse liability of products will be measured across several domains 1) smoking puff topography, 2) subjective effects, 3) behavioral economic choice tasks, and 4) craving for and suppression of craving and withdrawal. Smoking puff topography will be measured with CReSS Pocket Topography Device by Borgwaldt. The device uses a pressure transducer integrated into a plastic cigarette holder to produce measures of puff count, puff duration, inter-puff-interval, puff flow rate, average puff volume, and total puff volume. Puff topography is a validated and sensitive behavioral measure of abuse liability, is highly stable and associated with level of dependence and predicts level of exposure to harmful tobacco-related toxicants. An adapted version of the Drug Effects/Liking Questionnaire will assess the desire and liking of UBMC and all three study products, positive and negative effects (i.e., side effects), and perceived strength and effectiveness. [The modified Cigarette Evaluation Questionnaire (mCEQ) will also assess subjective responses to cigarettes (e.g., reward, satisfaction).] The Cigarette Purchase Task will ask participants how much they would be willing to pay (ranging from 0¢ to \$1,120) to smoke each product. Given that the study products will look similar to cigarettes, we will retain the original language (e.g., “1 cigarette”) in the purchase task. [Willingness to spend more will indicate greater abuse liability.] Smoking urges/craving will be measured using the Tiffany-Drobes Questionnaire of Smoking Urges: Brief Form. This is a 10-item measure where participants rate smoking-related items (“All I want right now is a cigarette.”) on a 7-point Likert scale ranging from ‘strongly agree’ to ‘strongly disagree’. Similar to previous studies, we will collapse the items into two previously identified factors (Factor 1: strong desire and intention to smoke; Factor 2: anticipation of relief from withdrawal symptoms). Nicotine withdrawal will be assessed using the empirically validated 15-item version of the Minnesota Nicotine Withdrawal Scale. This measure assesses smoking craving, anger/irritability, anxiety, depressed mood, restlessness/difficulty concentrating, increased appetite, sleep problems, and somatic symptoms (nausea, constipation, sore throat, dizziness, coughing). [Subjective effects (daily diary) of the Phase 2 substitute product will be derived from daily diaries assessing product satisfaction and pleasure.] [Substitutability of products will be assessed using a Cross-Price Task, a Progressive Ratio (PR) Task and daily diaries. A Cross-Price Task in Phases 1 and 3 will estimate substitutability of the study product for the UBMC. Participants will be asked how many study products and UBMCs they would consume when the price of the study product is fixed at \$1 and the UBMC prices escalate. The data are then fit to an exponential equation that indicates whether the fixed-price product substitutes for the primary product, and the degree of substitution. Cross price elasticity (CPE) for each study product compared to UBMC  $> 0.2$  indicates substitution,  $CPE <$

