### 2. Data Analytic Plan

Statistical analyses will be performed using SAS 9.4 and an alpha of .05. Background measures will be summarized by product (UBMC, mFLC, mRYO, nmC), as appropriate. Continuous variables will be presented as mean  $\pm$  SD; categorical variables will be presented as counts and proportions. We will apply a transformation to normalize the distribution and stabilize the variance of the residuals where appropriate.

Hypotheses 1a and 1c: We will use Repeated Measures Analysis of Variance with Tukey-adjustment to examine differences between the alternatives and the UBMC in abuse liability assessed at each product lab session. Assuming statistically significant product differences, this post-hoc test will allow us to not only compare each product to the UBMC, but will also allow comparison of the alternative products with each other. Because product introduction in Phase 1 will be randomized using a Latin Square, a fixed effect for session and a random effect for sequence will be included in all analyses.

Hypothesis 2a: Product preference will be examined using a Chi-Square Test, comparing the proportions of participants choosing each alternate product for further use.

Hypothesis 2b: We will examine the trajectory of use behavior outcomes using Linear Mixed Model (LMM) regression analysis. We will employ a random intercept or slope parameter, as appropriate, and model the covariance structure for the repeated outcome measures, while accounting for potential confounders, including gender and baseline cigarettes/day.

Hypothesis 2c: This aim will be analyzed as a Chi-Square Test of Goodness of Fit to test the proportion of use compared to 80%.

Hypothesis 3: We will examine whether differences in product characteristics and changes in perceived effects collected via daily diary are associated with increased substitution of the alternate product over the seven-day period using generalized LMM regression analysis, similar to that outlined in H2b.

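### The fall in craving and withdrawal predicted by H1a has no planned test: the one analysis named compares products with each other and does not say how the pre-smoking score or the post-smoking times enter

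*Combined protocol and SAP*

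**What the plan says.** Specific Aims, Aim 1 (H1a), predicts that the alternatives will "significantly reduce nicotine craving/withdrawal similar to UBMC". This has two parts: craving and withdrawal fall after each alternative is smoked, and the fall resembles that after the usual brand.

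The data for the first part are collected. Section D.2, Study Procedures, says that "self-report measures of craving and withdrawal will be recorded immediately before and at several times after the smoking session". Under Detailed Study Procedures, the subjective-effect measures "will be collected immediately before the onset of puffing and at 1-min, 15-min, 30-min, 60-min, and 90-min after completion of the cigarette". Section D.3, Measures, lists "craving for and suppression of craving and withdrawal" as an abuse-liability domain but does not define suppression as a change from the pre-smoking score.

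Section E.2, Data Analytic Plan, gives one analysis for Hypotheses 1a and 1c: "We will use Repeated Measures Analysis of Variance with Tukey-adjustment", used "to examine differences between the alternatives and the UBMC in abuse liability assessed at each product lab session". Pairwise comparisons follow if products differ significantly overall. Because of the Latin square, "a fixed effect for session and a random effect for sequence will be included in all analyses".

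**The concern.** A fall from before to after smoking is a within-product statement. The tests in section E.2 are all between products. A between-product test asks whether the products differ; it does not ask whether any of them did anything.

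This matters most when H1a is true. If all four products suppress craving alike, the expected result is a non-significant product effect, and the plan stops there because its pairwise comparisons depend on a significant one. A study in which no product suppressed craving would give the same result.

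Secondly, six scores per session (one before, five after) can be analysed as a level, a change, an average or a single time. The plan does not choose, so the choice could be made after the data are seen. It also does not say whether the pre-smoking score, already measured, will be used to remove session-to-session noise.

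**Working it through.** **The plan's own figures.** There is none to reproduce for craving or withdrawal. Section E.1 gives a mean and SD only for satisfaction (5.5 and 1.3, with 81% power at N = 80). That 81% does not reproduce for a 50% fall (2.75 points gives power above 99.9%), but this is a separate matter and nothing below depends on it.

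**Step 1: what each test can show.** A crossover was simulated with 80 participants (the N in section E.1), four products in a Latin square, participant effects, adjustment for session, and 1,000 runs. Assumptions: half of the variance lies between participants, the within-person pre-post correlation is 0.5, and two-sided alpha is 0.05. There was no true product difference.

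| True fall, all products | Product F-test, mean of all six scores | Product F-test, 1-minute score | Pre-post test significant in all four products |
|---|---|---|---|
| 0 | 4.3% | 3.7% | 0% |
| 1 SD | 4.6% | 4.6% | 100% |

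The product test does not distinguish the two situations. The within-product test does.

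**Step 2: precision of the product comparison.** Let r be the within-person correlation, across sessions, between the pre-smoking score and the post-smoking score analysed, with equal within-person variances. Relative to analysing a single post-smoking score alone, the variance of a product contrast is multiplied by:

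- 1 − r² with the pre-smoking score as covariate (a reduction of r²);
- 2(1 − r) with a raw change score.

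| Assumed r | 1 − r² | Reduction | 80 act like 80/(1 − r²) | 2(1 − r) |
|---|---|---|---|---|
| 0.1 | 0.99 | 1% | 81 | 1.8 |
| 0.3 | 0.91 | 9% | 88 | 1.4 |
| 0.5 | 0.75 | 25% | 107 | 1.0 |
| 0.7 | 0.51 | 49% | 157 | 0.6 |

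A raw change score helps only if r exceeds 0.5. It is always less precise than adjustment, by the factor 2(1 − r)/(1 − r²) = 2/(1 + r), which is 1.54, 1.33 and 1.18 at r = 0.3, 0.5 and 0.7.

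**Step 3: the same in power.** In the same simulation the usual brand was better by 0.3 SD at every post-smoking time. Power of the product test:

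| r | 1-minute score alone | With pre-score covariate | Change score | Mean of all six |
|---|---|---|---|---|
| 0 | 78% | 78% | 47% | 100% |
| 0.3 | 79% | 83% | 62% | 95% |
| 0.5 | 80% | 91% | 79% | 87% |
| 0.7 | 79% | 98% | 95% | 75% |

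The last column shows how far the answer depends on which scores enter. It relies on the simulated difference being constant over 90 minutes.

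**The case against.** **The plan is silent; it does not exclude.** A reader might infer that the model has no time term and discards the pre-smoking score. The text does not support that. Session and sequence are named as terms common to all analyses, in a paragraph that also covers topography, liking and demand. Repeated measures could include the within-session times, and suppression could be read as a change score. This stands, and the point is worded accordingly. It does not close the gap: on either reading, the tests named still compare products.

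**Arrival deprivation is not a bias.** A reader might infer that product contrasts are distorted by how deprived participants were on arrival. Product order is randomised, and every session follows 12 hours of abstinence verified by exhaled CO. Deprivation is therefore balanced in expectation, and what remains is noise. This stands in full.

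**The precision gain is assumed.** The documents give no pre-post correlation for craving or withdrawal. Verified abstinence may narrow the spread of pre-smoking scores and make r small, and the gain presumes that the plan would use a post-smoking score alone. This also stands: the gain could be close to nil.

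**The five post-smoking times.** The minute-by-minute schedule is stated for subjective effects, which section D.3 lists apart from craving and withdrawal. Section D.2 says only several times after smoking for the latter. That the same schedule applies is a fair inference, but the point needs only one score before and at least one after.

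**Conclusion.** The point holds as a gap between hypothesis and analysis. The reduction half of H1a's craving and withdrawal claim has no planned test, and this conclusion needs no assumed number. The plan also leaves open which post-smoking score is compared and how the pre-smoking score is used.

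The precision argument is secondary and conditional: a variance reduction of r², from 1% at r = 0.1 to 49% at r = 0.7, for a single post-smoking score otherwise analysed alone. The upper end should not be read as an expected gain. The argument covers craving and withdrawal only. Topography has no pre-smoking value and is unaffected. Whether a non-significant product difference can support similarity to the usual brand is a further question that this point does not settle.

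**What to change.** For craving (the two QSU-Brief factors) and withdrawal (MNWS), add to section E.2:

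1. **Reduction.** A mixed model with the pre-smoking score as one level of time. Fixed effects: product, time, product-by-time and session. Random effects: participant and the planned sequence effect. Test reduction by pre-to-post contrasts within each product. The pre-smoking score has to be a response here, because a pre-to-post change is not a contrast of a model fitted to post-smoking scores only, and the sampling error of the pre-smoking mean must be counted.
2. **Product comparison.** One post-smoking summary named in advance, for example the 90-minute average. Covariates: the session's pre-smoking score and the participant's mean pre-smoking score. Keep the planned session, sequence and Tukey terms. Do not use a raw change score.
3. **Schedule.** State that the 1- to 90-minute times apply to the QSU-Brief and MNWS, if that is intended.

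The cost is a paragraph of analysis-plan text and a few lines of model code. No new data, visits or participants are needed.

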**Aim 2: To assess the substitutability of menthol cigarette alternatives.** [*H2a: A significantly higher portion of product preference selections for Phase 2 will favor nmC than all other alternatives. H2b: Participants' use of study products will significantly increase over the one-week substitution period. H2c: Under simulated UBMC ban conditions, >80% of participants will substitute at least 50% of their UBMC use with study product.]*

**Aim 3: To evaluate which product characteristics and perceived effects influence greater substitution.** *H3: Participants reporting higher product satisfaction, including "throat hit", menthol-specific sensory effects,*

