## Addiction and Behavior Related to Menthol Cigarette Substitutes

*craving reduction, improved mood with use, and ease of use [on daily diaries, will report the greatest substitution of study product for UBMC.]*

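### H3 compares participants, but the planned diary model does not separate between-person from within-person effects or say which coefficient tests H3

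*Combined protocol and SAP*

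**What the plan says.** Under Aim 3 in the Specific Aims, H3 is worded across people: "Participants reporting higher product satisfaction", along with other favourable diary ratings, "will report the greatest substitution of study product for UBMC" (UBMC is the usual-brand menthol cigarette).

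Under Hypothesis 3 in the Data Analytic Plan, the analysis asks "whether differences in product characteristics and changes in perceived effects collected via daily diary are associated with increased substitution", with substitution followed over seven days. The model is described only by reference: "using generalized LMM regression analysis, similar to that outlined in H2b".

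The H2b text supplies the template: "We will employ a random intercept or slope parameter, as appropriate, and model the covariance structure for the repeated outcome measures". The adjustment variables it gives are sex and the number of cigarettes smoked daily at baseline. No other covariate or derived predictor is named.

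Table 1 lists satisfaction, liking, urge and withdrawal measures as Phase 2 diary items, so these perceptions can vary from day to day within a participant. The plan gives no centring rule, no person-mean term and no statement of which coefficient decides H3.

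**The concern.** The hypothesis and the analysis are pitched at different levels. H3 asks whether people who rate the product higher substitute more than people who rate it lower. The analysis text speaks of changes in perceived effects, which points to movement within a person from day to day. In a mixed model on daily data these are two different slopes, and they can differ in size or sign.

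A programmer working from the H2b template could reasonably enter the raw daily score once. The resulting coefficient would be a weighted average of the two slopes. The write-up could then report a day-level association as evidence about who substitutes, or report no association when one exists between people. H3 is the only hypothesis under Aim 3, so the aim's conclusion depends on this choice. The exploratory age-by-predictor terms would carry the same ambiguity.

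**Working it through.** The documents give no power, effect size or ICC for H3 (the Power Analysis section covers H1a and H2c only), so there is no stated figure to reproduce. The check asks what a single uncentred coefficient would estimate.

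**Inputs from the documents.** T = 7 diary days per participant in Phase 2; 80 participants analysed (Power Analysis); alpha 0.05, taken as two-sided.

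**Assumptions.** Linear random-intercept model with a daily outcome; predictor ICC rx and residual outcome ICC ry, both varied because neither is given.

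**Formula.** The generalised least-squares coefficient is w × (within-person slope) + (1 − w) × (slope on observed person means), where

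- W = (T − 1)(1 − rx)
- λ = (1 − ry) / (1 − ry + T·ry)
- B = λ(T·rx + 1 − rx)
- w = W / (W + B)

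**At rx = ry = 0.5.** W = 6 × 0.5 = 3. λ = 0.5 / (0.5 + 3.5) = 0.125. B = 0.125 × (3.5 + 0.5) = 0.5. So w = 3 / 3.5 = 0.857.

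**Ends of the 0.3 to 0.7 range.**

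- rx = 0.7, ry = 0.3: W = 1.8, λ = 0.25, B = 0.25 × 5.2 = 1.3, w = 1.8 / 3.1 = 0.58.
- rx = 0.3, ry = 0.7: W = 4.2, λ = 0.3 / 5.2 = 0.058, B = 0.058 × 2.8 = 0.16, w = 0.96.

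**Within-person weight over a wider range.**

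| rx | ry = 0.1 | ry = 0.3 | ry = 0.5 | ry = 0.7 |
|---|---|---|---|---|
| 0.3 | 0.73 | 0.86 | 0.92 | 0.96 |
| 0.5 | 0.57 | 0.75 | 0.86 | 0.93 |
| 0.7 | 0.38 | 0.58 | 0.74 | 0.86 |
| 0.8 | 0.27 | 0.45 | 0.62 | 0.78 |
| 0.9 | 0.14 | 0.27 | 0.43 | 0.62 |

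The weight drops below one half once rx exceeds 0.58, 0.77, 0.87 or 0.94 for ry = 0.1, 0.3, 0.5 or 0.7.

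**Effect on the test.** Simulation with 80 participants, 7 days, 2,000 replicates, unit total variances for the predictor and for the outcome residual, and known variance components for the single-term model. Each cell gives the mean estimate and the share of runs significant.

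| rx, ry | True between slope | True within slope | Single term | Person-mean term |
|---|---|---|---|---|
| 0.5, 0.5 | 0 | 0.3 | 0.26, 100% | 0.04, 6% |
| 0.5, 0.5 | 0.4 | 0 | 0.05, 20% | 0.35, 86% |
| 0.8, 0.3 | 0 | 0.3 | 0.15, 70% | 0.01, 5% |
| 0.8, 0.3 | 0.4 | 0 | 0.21, 94% | 0.39, 100% |

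In the last two rows the within-person weight is only 0.45. The single term still appears to support H3 in 70% of runs with no between-person effect.

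**The case against.** A reader might infer that the plan has committed to one coefficient per perception and that this coefficient mostly measures within-person association. The documents support neither part. The Hypothesis 3 text names a model family and is silent on coding; a model with a person mean and a daily deviation is also a generalized LMM. Whether the blend is mainly within-person depends on ICCs that are not given, and nothing rules out ratings of one product being stable enough over a week to put the weight below one half.

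A reader might also infer that Aim 3 is being answered with simply the wrong quantity. That goes too far:

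- The Innovation section wants the diaries to show day-by-day mechanisms of substitution, and the analysis text refers to changes. Within-person association is therefore a legitimate secondary question.
- Each participant uses one chosen product in Phase 2. A characteristic fixed by product is constant within a person, so its coefficient is already between-person.
- The H2b template allows random slopes, and H3 may use a non-linear link. The weights above would then change, although the blending would remain.
- A single term is not always worse at detecting something. With both ICCs 0.5, a between slope of 0.4 and a within slope of 0.1, it is significant in 91% of runs against 87% for the person mean. Its estimate of 0.14 is nevertheless far from 0.4.

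All of these limits stand. They narrow the point to under-specification, with a mismatch between the wording of H3 and the wording of its analysis. They do not remove it, because at any intermediate weight one coefficient does not isolate the slope that H3 names.

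**Conclusion.** The point holds as a gap in specification and should be fixed before analysis. H3 is between-person; its planned analysis neither separates the two levels nor says which coefficient is the test. If a time-varying perception is entered once and uncentred, the within-person share is 86% at ICCs of 0.5 and 58% to 96% for ICCs from 0.3 to 0.7. It falls below half when perceptions are very stable and outcome clustering is low. In the simulated cases H3 could be supported with no between-person effect (70% to 100% of runs) or a real one missed (20% power against 86% at ICCs of 0.5). These figures rest on a linear random-intercept model, seven complete diaries and assumed ICCs. Product-fixed predictors are unaffected.

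**What to change.** Add to the Hypothesis 3 paragraph that, for each time-varying diary perception, two terms enter the model: the participant's mean over completed Phase 2 diaries, and the daily deviation from that mean. Report both. State that the H3 conclusion rests on the person-mean term and that the deviation term addresses the day-by-day mechanism question raised in the Innovation section. Say which of the two terms the exploratory age interaction applies to, or apply it to both. Leave product-fixed characteristics as single terms.

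The cost is SAP wording and two derived variables per perception; no new data or visits are needed. There are two small downsides. The model gains one extra term per perception. The person mean is also a noisy measure of a participant's usual level, so it slightly attenuates the slope. With rx = 0.5 and 7 diaries the factor is 0.5 / (0.5 + 0.5/7) = 0.875, which turns a true 0.40 into 0.35, as in the simulation. With 5 completed diaries it is 0.5 / (0.5 + 0.5/5) = 0.833, giving 0.33. The report should therefore state how many diaries contributed to each mean.
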